This primary outcome measures changes in number of migraine days per month before and during treatment. The number of migraine days per month will be captured using a validated headache questionnaire and scores as follows: 0-8 migraine days per month = low frequency episodic migraine, 9-14 migraine days per month = high frequency episodic migraine, 15-30 migraine days per month = chronic migraine.

[figure not shown]
Assessments of headache and sleep:

At screening (visit 1), headache severity and impact will be assessed based on patients' interviews and HIT-6. Sleep quality will be assessed using the Insomnia Severity Index.

(<https://cbtscience.files.wordpress.com/2014/02/insomniaseverityindex.pdf>).

On days 30, 60, 90 and 120, baseline and treatment impact on headache and sleep will be assessed using the Headache e-diary and the consensus sleep diary [Carney et al., (2012) *The consensus sleep diary: Standardizing prospective sleep self-monitoring*, Sleep Vol.35, No.2, pp.287-302], the latter of which captures total sleep time, sleep latency, wake after sleep onset, number of awakenings, quality, sleep efficiency, and trouble staying awake.

Study flow chart

B. Statistical Considerations

Sample Size Justification:

Although precise sample size calculations are difficult given the novelty of the hypotheses and hierarchical structure of the data, a simulation was created using the “SIMR” package in R and R-Studio. Enrolling $N = 100$ with 4 measurement occasions (baseline, M1, M2, M3) that are created by aggregating the daily measurements from each month provides sufficient power to detect even small associations between changes in sleep and migraine activity. For example, fitting a linear mixed effects model assuming a random intercept, a modest association between intercept and slope ($r = -0.50$), unit variances for the fixed and random effects (i.e., z-scores), and $\alpha = 0.05$, this sample size will provide 95% power (95%CI: 75.1% to 99.9%) to detect correlations between slopes (i.e., changes in migraine and sleep) as small as $r = 0.15$. Differences smaller than this magnitude are unlikely to be clinically meaningful.

Data Analysis:

To fulfill the study’s purpose, 4 hypothesis are being proposed:

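### The stated 95% power for a slope correlation of 0.15 with N = 100 does not follow: two-sided power is about 24% to 32%, and no slope-correlation reading examined reaches the plan's own lower limit of 75.1%

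*Combined protocol and SAP*

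**What the plan says.** The claim is in B3, section B (Statistical Considerations), under Sample Size Justification. It reports a simulation in the SIMR package with 100 participants and four occasions (baseline, M1, M2, M3), each "created by aggregating the daily measurements from each month". The model is described as "fitting a linear mixed effects model assuming a random intercept". The same sentence adds an intercept-slope correlation of -0.50, variances of 1 for fixed and random effects, and alpha of 0.05. It concludes that "this sample size will provide 95% power (95%CI: 75.1% to 99.9%) to detect correlations between slopes" as small as 0.15, and the paragraph ends: "Differences smaller than this magnitude are unlikely to be clinically meaningful".

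The paragraph gives no number of simulation runs, sidedness, residual variance or drop-out allowance. The Data Analysis text that follows plans individual-level random effects for both the pre-treatment values and the change parameters of each outcome.

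**The concern.** A correlation between person-level slopes is a between-person quantity. Four occasions per person measure each slope better, but they do not turn 100 pairs of slopes into 400. A correlation of 0.15 in 100 people is usually hard to detect, so 95% power is surprising on its face. The interval, nearly 25 percentage points wide, also suggests very few simulation runs.

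This figure is the only numerical support for N = 100, and the study's main goal is the link between migraine prevention and sleep improvement. A reader who accepts 95% power at 0.15 would take a non-significant result as good evidence against any association of that size or larger.

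**Working it through.** **Inputs from the plan.** N = 100; four occasions, coded 0 to 3, so the sum of squares of time about its mean is 5 per person; alpha 0.05; slope correlation 0.15; intercept-slope correlation -0.50; random-effect variances of 1.

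**Assumed.** Two-sided testing, with one-sided also shown. Residual variance 1, with a range shown.

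**1. The printed interval.** Exact (Clopper-Pearson) 95% limits for 19 of 20 are 75.13% and 99.87%, which round to the printed 75.1% and 99.9%. Among all k/n with n from 5 to 3,000 and a proportion that rounds to 95%, no other pair matches. Wilson limits for 19/20 are 76.4% and 99.1% and do not match.

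**2. Power with error-free slopes.** By Fisher's z, power is Φ(atanh(r) × √(N − 3) − z), plus a negligible opposite tail. Here atanh(0.15) × √97 = 0.1511 × 9.849 = 1.489.
- Two-sided: Φ(1.489 − 1.960) = 31.9%.
- One-sided: Φ(1.489 − 1.645) = 43.8%.

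**3. Power with measurement error in the slopes.** With residual variance 1, the error variance of a person's slope is 1/5 = 0.2. Reliability is 1/(1 + 0.2) = 0.833, and the observed correlation becomes 0.15 × 0.833 = 0.125. Two-sided power is then 23.6%. With residual variance from 0.25 to 4 times the slope variance, power runs from 29% down to 13%.

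**4. Check by simulation.** A bivariate model with random intercepts and slopes for both outcomes and residual variance 1 was tested with a likelihood ratio test of the slope-slope covariance (400 runs per setting). It gives 21% to 23% with all cross-outcome covariances estimated, and 32% to 44%, depending on time coding, with the other cross-outcome covariances fixed at zero.

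**5. A more favourable conditional reading.** If both intercepts are known without error and are independent across outcomes, each slope's remaining variance is 1 − 0.50² = 0.75. The partial correlation is 0.15/0.75 = 0.20, with power of about 51.5%. Even at that power, 19 or more successes in 20 runs would have a probability of about 3 in 100,000. At 32% it would be about 6 in a billion.

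**6. Where larger values do appear.** They appear only when something else is tested.
- All 400 person-months treated as independent: 85% two-sided, 91% one-sided.
- A fixed slope coefficient of 0.15 with no random slope: SE = √(1/(5 × 100)) = 0.0447 and 0.15/0.0447 = 3.354, so power is 91.8% two-sided and 95.6% one-sided.
- The same coefficient with a unit-variance random slope: SE = √(1.2/100) = 0.1095, and two-sided power falls to 28%.

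**7. What N = 100 can detect (two-sided).**

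| Power | Error-free slopes | Residual variance 1 (divide by 0.833) |
|---|---|---|
| 50% | tanh(1.960/9.849) = 0.196 | 0.236 |
| 80% | tanh((1.960 + 0.842)/9.849) = 0.277 | 0.332 |

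**8. N needed at 0.15 (two-sided).** With error-free slopes, ((1.960 + 0.842)/0.1511)² + 3 is about 347 for 80% power; replacing 0.842 by 1.645 gives about 572 for 95%. With residual variance 1, using atanh(0.125) = 0.1257, the figures are about 500 and 826.

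**The case against.** The strongest defence is that the plan calls precise calculation difficult and offers the figure as an example. The primary hypotheses are to be tested with lagged and synchronous terms, fixed effects, interactions and nested likelihood ratio tests, not with one slope-slope correlation. That stands as a limit on the conclusion. A reader might infer that the primary analyses have 24% to 32% power. The documents do not show this, because no power is given or derivable for the lagged models.

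Other tempting readings also go too far:
- **That 32% is a ceiling.** Sidedness is not stated, and one-sided or constrained variants reach about 44% to 52%.
- **That the simulated model had no person-level slopes.** The text names a random intercept, but the intercept-slope correlation in the same sentence implies a random slope. The description is unclear; it is not shown to lack slopes.
- **That the 95% came from testing a fixed coefficient.** The match at 92% to 96% is suggestive, but the documents do not identify the source. It remains conjecture.
- **That 20 runs is a documented fact.** It is an inference that requires the interval to be exact binomial.
- **That correlations up to 0.28 to 0.33 would usually be missed.** Those are the 80% power points, so they would usually be found.

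None of this rescues the 95%. The plan names the quantity, sample size, alpha and effect size, and every reading examined that tests a slope correlation falls short of 75.1%. Difficulty of calculation excuses imprecision, not a threefold overstatement.

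**Conclusion.** Wrong as written. For the quantity that the plan names, two-sided power is about 32% with error-free slopes and about 24% with residual variance 1, against a stated 95%. The lower figure depends on the assumed residual variance; both depend on two-sided testing without constraints on the other covariances. Relaxing those conditions gives at most about 52% among the variants examined, so the conclusion does not depend on them.

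The practical consequence lies between 0.15 and about 0.20 to 0.24. The plan does not rule out correlations in that range as clinically meaningful, yet at N = 100 they would be missed more often than found. Any drop-out would lower power further: with an assumed 20% loss (N = 80), power at 0.15 is about 26% even with error-free slopes.

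**What to change.** 1. Rerun the simulation with at least 1,000 replicates of a bivariate model with random slopes for both outcomes, to match the random change parameters in the Data Analysis text, and test the slope-slope covariance.
2. Report the tested parameter, sidedness, residual variance, drop-out assumption and number of runs.
3. Replace the 95% figure and its interval with the result. Two-sided, about 24% to 32% at a correlation of 0.15 is to be expected, with 80% power at about 0.28 to 0.33.
4. Delete the phrase that claims enough power for even small associations, and state that a non-significant result does not exclude a correlation of 0.15.

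This takes a few hours of simulation and a change of protocol wording. The only downside is a less favourable stated figure. Whether to keep N = 100 once the figure is corrected is for the sponsor to decide.

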Hypothesis 1 – temporal relationship I: Fremanezumab partially prevents migraine by restoring some aspects of sleep disturbances. If this hypothesis is correct, fremanezumab-induced improvement in sleep disturbances will precede the improvement in headache (i.e., the reduction in migraine days per month).

Hypothesis 2 – temporal relationship II: Fremanezumab-induced improvement in sleep disturbances is secondary to the reduction in migraine days per month. If this hypothesis is correct, fremanezumab-induced reduction in migraine or headache days per month will precede the onset of improvement in sleep quality and quantity.

Hypothesis 3 – principle III: The prevention of migraine leads to improved sleep and reduced sleep disorders. If this hypothesis is correct, only fremanezumab responders will experience improved sleep or sleep disturbances whereas fremanezumab non-responders will not experience improvement of sleep disturbances. If this hypothesis is incorrect, sleep quality or quantity will not improve in fremanezumab responders.

Hypothesis 4 – principle IV: Fremanezumab-Improved sleep disturbances lead to reduced migraine or headache days per month. If this hypothesis is correct, only persons with improved sleep disturbances will experience reduction in number of migraine or headache days per month. If this hypothesis is incorrect, patients with improved sleep disturbances may be migraine treatment responders.

[figure not shown]
The primary analyses are designed to estimate the elements of the competing hypotheses (i.e., temporal changes in migraine and sleep). To contrast these hypotheses, we will employ multivariate multilevel regression models as summarized by MacCallum et al.⁷³ and Goldstein.⁷⁴ This approach to modeling within-person change does not have the limitations of a change score approach (i.e., unreliability of residualized change scores), or percentage change approaches (i.e., floor effects, heterogeneous variances) where predictors and outcomes are reduced to differences among measurement occasions. A multivariate modeling approach will allow a direct test of all study hypotheses while maintaining a conservative Type-I error rate. Briefly, parsimonious models will be specified for outcomes and lagged (Y_{t-1}) and synchronous (Y_t) representations of each of the proposed mechanisms modeling time with both linear and quadratic change parameters. This model form will

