capture the expected substantial early-treatment changes in mechanisms (emerging via reductions in daily headache probability and/or increased sleep quality), or more gradual changes that may occur over the full treatment period. The pre-treatment values and change parameters will be specified as individual-level random effects; this effectively allows a unique trajectory to be specified for each individual and for each outcome. These trajectories will then be aggregated using a series of fixed main effects and interactions that directly correspond to each of our specific hypotheses.

In hypothesis 1, lagged sleep trajectories (t-1, t-2, and t-3) are hypothesized to exhibit statistically significant associations with headache probability such that greater increases in sleep are associated with greater reductions in migraine activity. The opposite is assumed in hypothesis 2 where lagged headache trajectories are hypothesized to exhibit statistically significant associations with sleep such that greater reductions in migraine activity are associated with greater increases in sleep. The best fitting model, using lags of either/both will be estimated using nested models and likelihood ratio tests to evaluate the best fitting hypothesis.

Secondary analyses: In addition to testing primary hypotheses, this study will provide a rich source of data to examine effects on other mechanisms. First, analyses will consider questions of “for whom does treatment work?” We will test whether pre-treatment levels of outcomes lead to differential response to treatments (ie, association between intercepts and slopes), which could provide preliminary evidence that, for instance, individuals with worse sleep respond best to treatment. Second, we will estimate the primary models using additional dichotomizations such as ‘responders’ for both sleep and migraine activity (> 50% change). For these analyses, treatment phase (baseline, treatment) and responder (no, yes) will be fixed factors with associations between response groups evaluated using frequency counts and odds ratios (95%CI). In a final set of models, we will use three treatment phases (baseline, early treatment, late treatment) to examine the cross-lagged association of responders and non-responders by treatment phase.

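### Hypotheses 3 and 4 each rest on an absence of change in a comparison group, but the plan gives no criterion for absence and no refutation rule that works

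*Combined protocol and SAP*

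**What the plan says.** All references are to the combined protocol and SAP, section B3.B (Statistical Considerations), unless stated.

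- **Hypothesis 3 (Data Analysis).** Migraine prevention leads to better sleep. If so, sleep improves in responders only, "whereas fremanezumab non-responders will not experience improvement of sleep disturbances". The refutation follows: "If this hypothesis is incorrect, sleep quality or quantity will not improve in fremanezumab responders".
- **Hypothesis 4 (Data Analysis).** Better sleep leads to fewer migraine days. If so, "only persons with improved sleep disturbances will experience reduction in number of migraine or headache days per month". It is said to be incorrect if patients whose sleep improved may turn out to be migraine responders.
- **Primary models (Data Analysis).** Individual trajectories are combined through main effects and interactions said to match each hypothesis. Explicit criteria follow for Hypotheses 1 and 2 only: significant lagged associations, compared by likelihood ratio tests on nested models.
- **Secondary analyses.** Responders, for sleep and for migraine, are defined by more than 50% change. Phase and responder status are fixed factors, with "associations between response groups evaluated using frequency counts and odds ratios (95%CI"). Further models compare responders and non-responders across three treatment phases.
- **Sample Size Justification.** N = 100 with four monthly occasions is said to give 95% power for a correlation of 0.15 between sleep and migraine slopes. The text adds: "Differences smaller than this magnitude are unlikely to be clinically meaningful".

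**The concern.** Each of these hypotheses has two halves: one group changes and the other does not. A test against zero can support the first half. The second half is a no-effect claim in part of a 100-patient study, and it needs a statement of how small a change counts as none. Without one, a non-significant result in a small group can be read as absence.

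The refutation clauses do not guard against this, because neither looks at the comparison group. Equal improvement in both groups is a realistic outcome. Section B2 proposes that the drug may act on sleep through the hypothalamus, and such an effect need not depend on migraine response. The design in B3.A has no control arm, so non-specific improvement would also appear in both groups. At stake is the mechanistic conclusion: a sleep effect common to all patients could be reported as one that occurs only where migraine was prevented.

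**Working it through.** **1. The stated rules set against the possible outcomes of Hypothesis 3**

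| Responders' sleep | Non-responders' sleep | Stated condition for correct | Stated condition for incorrect |
|---|---|---|---|
| improves | no change | met | not met |
| improves | improves | not met | not met |
| no change | no change | not met | met |
| no change | improves | not met | met |

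The second row contradicts the claim that only responders improve, yet nothing in the plan refutes the hypothesis there. Rows one and two differ only in whether non-responders changed, which is the judgement that has no criterion.

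For Hypothesis 4, the outcome that should refute it is a fall in migraine days among people whose sleep did not improve. The stated clause instead names improved sleepers who respond on migraine, which is what Hypothesis 4 predicts. If a negative was intended there, the clause would still not look at the comparison group.

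**2. The plan's own power figure**

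The stated 95% (95% CI 75.1% to 99.9%) concerns a correlation of slopes in all 100 patients. A Fisher z approximation does not reproduce it: Φ(atanh(0.15) × √97 − 1.96) = Φ(1.489 − 1.960) = 32%. The stated interval equals the exact interval for 19 successes in 20 simulated runs. The simulation inputs are not fully given, so this does not show that the figure is wrong. It has no bearing on change within a subgroup.

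**3. Illustration: separate within-group tests when both groups improve equally**

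From the plan: N = 100 and α = 0.05. Assumed: two-sided paired t-tests, SD of change = 1 in both groups, 30 to 60 non-responders, no dropout, and a true improvement of 0.3 or 0.5 SD in both groups. Power comes from the noncentral t distribution.

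Chance of the pattern = power in responders × (1 − power in non-responders).

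| Non-responders / responders | Missed in non-responders, 0.3 SD | Power in responders, 0.3 SD | Pattern, 0.3 SD | Missed in non-responders, 0.5 SD | Pattern, 0.5 SD |
|---|---|---|---|---|---|
| 60 / 40 | 37.2% | 45.7% | 17% | 3.2% | 3% |
| 50 / 50 | 45.2% | 54.8% | 25% | 6.6% | 6% |
| 40 / 60 | 54.3% | 62.8% | 34% | 13.1% | 13% |
| 30 / 70 | 64.5% | 69.7% | 45% | 24.6% | 24% |

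Example, last row at 0.3 SD: 0.697 × 0.645 = 0.449. A direct two-sided test of the group difference would be wrong about 5% of the time in the same situation.

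**4. What a proper criterion could deliver**

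Chance that the upper 95% limit in non-responders lies below margin m when their true change is zero: Φ(m√n − 1.96).

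- m = 0.3 SD: n = 30 gives Φ(1.643 − 1.960) = 38%; n = 60 gives Φ(2.324 − 1.960) = 64%.
- m = 0.5 SD: n = 30 gives Φ(2.739 − 1.960) = 78%; n = 60 gives Φ(3.873 − 1.960) = 97%.

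Power of the responder-by-phase interaction for a 0.3 SD difference in change: Φ(0.3/√(1/n₁ + 1/n₂) − 1.96). With 30 and 70 patients this is Φ(1.375 − 1.960) = 28%; with 50 and 50 it is Φ(1.500 − 1.960) = 32%.

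**The case against.** The strongest reply is that the plan nowhere says Hypothesis 3 is confirmed by a non-significant test in non-responders. It signals interactions matched to each hypothesis, enters phase and responder as factors, reports 95% CIs for the odds ratios, and prefers multilevel models to change scores. That stands. The separate-test reading is left open, not prescribed, and naming the interaction largely clarifies a structure already indicated. What the reply does not supply is a named term or decision rule for Hypotheses 3 and 4. An odds ratio between response groups shows association; it does not bound the change in one group.

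A second reply is that equal improvement contradicts the only-responders wording anyway. That is true for a careful reader, but the explicit refutation sentence says otherwise and should agree with it.

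A third is that the responder analyses are secondary and the explicit model comparison is between Hypotheses 1 and 2. This limits the damage: a Hypothesis 3 pattern would not by itself rule out a direct sleep effect. A figure placed after the hypotheses is also not visible, so the gap can be claimed only for the readable text.

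Three stronger inferences are not supported:

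- A reader might take the 37% to 65% miss rate at 0.3 SD as the rate of false confirmation. It is not, because responders must also improve; the matching figure is 17% to 45%.
- A reader might convert a correlation of 0.15 to about 0.30 SD and call that the plan's meaningful sleep change. The plan attaches clinical meaning to a correlation between slopes, and the conversion applies to two independent groups, not to change within one group.
- A reader might treat the group sizes as planned. No responder rate is given.

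**Conclusion.** The point holds as a gap in the decision rules. Hypotheses 3 and 4 need evidence of absence in a comparison group. The readable plan does not say how absence will be judged, and both refutation clauses fail on the plan's own wording. That part needs no assumed number.

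The size is conditional. If separate two-sided paired tests were used, equal improvement would produce the Hypothesis 3 pattern in about 17% to 45% of trials at 0.3 SD and 3% to 24% at 0.5 SD, for 60 down to 30 non-responders of 100. The effect sizes, group sizes, unit SD of change and form of test are all assumptions. No separate figures were calculated for Hypothesis 4. The change should be made before analysis; the gap does not invalidate the study.

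**What to change.** In B3.B, Data Analysis and Secondary analyses:

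1. Name the responder-by-phase interaction on a stated sleep measure, with its 95% CI, as the test of Hypothesis 3, and require it for support.
2. Claim that non-responders do not improve only if the upper limit of the 95% CI for their sleep improvement lies below a pre-set margin, justified on the sleep scale used. Otherwise report the result as inconclusive.
3. Reject the claim that only responders improve whenever the lower 95% limit of improvement in non-responders is above zero. Do not also require that the groups show no difference, since that would be another absence claim without a bound. Report the interaction estimate separately.
4. Rewrite the Hypothesis 4 clause on its own terms. Reject it if migraine days fall (lower 95% limit of the reduction above zero) in people whose sleep did not improve. Require the sleep-improver-by-phase interaction on migraine days for support.

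The cost is wording and named model terms, with no new patients or data. The price is more inconclusive results. With 30 to 60 non-responders and no true change, absence would be shown about 38% to 64% of the time with a 0.3 SD margin, or 78% to 97% with a 0.5 SD margin. The interaction has only about 28% to 32% power for a 0.3 SD difference. The plan should state these limits.

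### The stated falsifier of Hypothesis 4 is what Hypothesis 4 itself predicts, that of Hypothesis 3 is incomplete, and the plan names no cell or model term that decides between them

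*Combined protocol and SAP*

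**What the plan says.** Data Analysis in section B3.B sets out four hypotheses. Two of them are 'only' statements about who improves.

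- **Hypothesis 3** (migraine prevention leads to better sleep) predicts that "only fremanezumab responders will experience improved sleep or sleep disturbances whereas fremanezumab non-responders will not experience improvement of sleep disturbances". Its falsifier is: "If this hypothesis is incorrect, sleep quality or quantity will not improve in fremanezumab responders".
- **Hypothesis 4** (better sleep leads to less migraine) predicts that "only persons with improved sleep disturbances will experience reduction in number of migraine or headache days per month". Its falsifier is: "If this hypothesis is incorrect, patients with improved sleep disturbances may be migraine treatment responders".

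The same section says that multivariate multilevel models will test all the hypotheses directly. It writes out the lagged terms only for Hypotheses 1 and 2.

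Secondary analyses then define responders "for both sleep and migraine activity (> 50% change"), with "associations between response groups evaluated using frequency counts and odds ratios (95%CI"). A last set of models uses three treatment phases "to examine the cross-lagged association of responders and non-responders by treatment phase".

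**The concern.** A falsifier should describe something that cannot happen, or is unlikely, if the hypothesis is true. The one written for Hypothesis 4 describes patients who improve on both outcomes, and Hypothesis 4 needs such patients to exist. Anyone applying the sentence as written learns nothing about Hypothesis 4. The finding that would count against it is written nowhere.

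Hypothesis 3 has a milder form of the problem. Its falsifier covers responders whose sleep does not improve but is silent on non-responders whose sleep does. That omission matters here. The Significance section proposes that the drug may act on hypothalamic neurons that regulate sleep, and such an action could improve sleep in a patient whose migraine does not respond.

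The responder analysis does not fill the gap by itself. Its only measure of association is one that cannot tell the two hypotheses apart. The rule for reading the counts would then be chosen after the data are seen, for two of the four stated hypotheses.

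**Working it through.** The plan gives no figure for this comparison, so there is none to reproduce. Its one computed figure, the power for a slope correlation, does not bear on the point.

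**Notation.** Cross-classify patients by migraine response and sleep response, using the plan's cut of more than 50% change:

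| | Sleep improved | Sleep not improved |
|---|---|---|
| Migraine responder | a | b |
| Migraine non-responder | c | d |

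**Step 1: predictions and falsifiers side by side.**

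| | Prediction | Observation that contradicts it | Falsifier as written |
|---|---|---|---|
| Hypothesis 3 | c = 0, and sleep improves in responders | c > 0, or no sleep improvement in responders | No sleep improvement in responders: valid, but c > 0 is missing |
| Hypothesis 4 | b = 0 | b > 0 | a may be above 0: also expected if Hypothesis 4 is true |

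**Step 2: the odds ratio.** OR = ad/(bc). Exchanging b and c leaves the product bc, and so the OR, unchanged. For example, a = 30, b = 20, c = 5, d = 45 gives 30×45/(20×5) = 13.5. With b = 5 and c = 20 it is 30×45/(5×20) = 13.5 again. This example shows only the symmetry. Both discordant cells exceed zero, so both strict predictions fail before and after the exchange.

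**Step 3: the two hypotheses exactly true.** N = 100 is the planned enrolment. The split into cells is an assumption. Because one cell is zero, 0.5 is added to each cell.

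- Hypothesis 3 true (a, b, c, d = 35, 15, 0, 50): OR = (35.5×50.5)/(15.5×0.5) = 231.3.
- Hypothesis 4 true (35, 0, 15, 50): OR = (35.5×50.5)/(0.5×15.5) = 231.3.
- The standard error of log OR is √(1/35.5 + 1/15.5 + 1/0.5 + 1/50.5) in both cases, so the 95% CI is 13.4 to 3994 in both.

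The value 231.3 depends on the assumed split. The equality does not.

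**Step 4: what separates them.** The two conditional proportions from the same tables:

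| | Hypothesis 3 true | Hypothesis 4 true |
|---|---|---|
| P(sleep improved given migraine non-responder) = c/(c+d) | 0/50 = 0% | 15/65 = 23% |
| P(migraine responder given sleep not improved) = b/(b+d) | 15/65 = 23% | 0/50 = 0% |

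**Step 5: precision of an empty cell.** For 0 of 50, the exact two-sided 95% upper limit is 1 − 0.025^(1/50) = 7.1%. An empty cell is therefore compatible with a true proportion of up to about 7%.

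**Step 6: why comparing b with c does not show direction.** The migraine response rate is (a+b)/N and the sleep response rate is (a+c)/N. Their difference is (b−c)/N, so a McNemar test compares only the two marginal rates. Suppose the outcomes are independent, with 60% migraine responders and 30% sleep responders among 100 patients. The cells are 18, 42, 12, 28 and OR = 18×28/(42×12) = 1.0, yet exact McNemar for 42 against 12 gives p = 0.00005. The asymmetry comes from the cut-points alone.

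**The case against.** A reader might infer that neither Hypothesis 3 nor Hypothesis 4 can be confirmed or refuted under this plan. The documents do not support that. Secondary analyses promise frequency counts as well as odds ratios, and the counts show b and c separately. At the chosen cut-point, any c above zero contradicts strict Hypothesis 3 and any b above zero contradicts strict Hypothesis 4. Hypothesis 3 also has a usable falsifier.

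A reader might also take the odds ratio to be the deciding test of the two hypotheses, so that a positive value would support both and, by the written sentence, count against Hypothesis 4. The plan does not say this. The odds ratio is secondary, the multilevel models are said to test every hypothesis, and the cross-lagged responder models address order in a way that a single 2×2 table cannot. The Hypothesis 4 sentence says only that improved sleepers *may* be responders, which makes it uninformative rather than a rule that turns a positive result into evidence against the hypothesis.

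These objections limit the reach of the point but do not remove it. The Hypothesis 4 falsifier is still compatible with the hypothesis. The odds ratio is still blind to which discordant cell is empty. The claim of a direct test for all hypotheses is still not backed by a named term, cell or decision rule for Hypotheses 3 and 4.

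**Conclusion.** The concern holds in limited form. The Hypothesis 4 falsifier is wrong as written, which follows from the text alone. The Hypothesis 3 falsifier is valid but covers half of the prediction. The responder odds ratio cannot by itself distinguish the two hypotheses, which is a matter of algebra. The planned counts can contradict either strict claim, but the plan does not say which count or model term bears on which hypothesis.

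The size is shown by the mirrored tables: the same OR under either hypothesis, against 0% and 23% exchanging places in the two conditional proportions. Those percentages rest on assumed response rates, since the plan gives none. They also rest on the cut of more than 50% standing for improvement. A patient with a smaller gain in sleep would be counted as not improved, so an occupied discordant cell speaks against the 'only' claim as dichotomised, not against every reading of it.

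The correction should be made before analysis. Nothing here calls the primary lagged models for Hypotheses 1 and 2 into question.

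**What to change.** 1. Reword the Hypothesis 4 falsifier along these lines: *if incorrect, migraine or headache days will also fall in patients whose sleep did not improve.*
2. Add to the Hypothesis 3 falsifier: *or sleep improves in non-responders.*
3. Keep the odds ratio as a description of association. Beside it, report P(sleep improved given migraine non-responder) for Hypothesis 3 and P(migraine responder given sleep not improved) for Hypothesis 4, each with an exact 95% CI. Name the sleep measure to which the cut of more than 50% applies.
4. State which of these proportions, and which model term if any, bears on Hypothesis 3 and which on Hypothesis 4.
5. Leave temporal direction to the lagged and cross-lagged models. Do not use a McNemar comparison of the discordant cells to infer it.

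The cost is SAP wording and a small extra analysis. No new data are needed.
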